9.4 Vital Signs

Vital signs measurements (blood pressure, and heart rate, respiratory rate and oral temperature) will be performed at screening, on Day 0, Day 1, Day 3, Day 7, Day 14, Day 28, and Day 112.

Descriptive statistics (mean, median, SD, Min, Max, and sample size) will be presented overall for screening and by the associated current treatment for on-study measurements and each vital sign measurement. Descriptive statistics for change from baseline for on-study measurements will also be presented. Baseline will be defined as the last results (scheduled or unscheduled) obtained prior to the first study vaccine administration. Results from on-study repeat tests will not be included in the summary statistics unless the repeat was required (and documented as such) due to technical reasons or an invalid initial result.

A listing of all vital signs results will be provided.

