### **3.5 Medicinal Product and Study Drug Administration**

There are four substances administered as part of this study. There are two study drugs SYN023 and rabies immune globulin (RIG): HyperRab ST® Grifols. SYN023 is investigational agent that has been administered previously to human subjects in a Phase 1 trial. RIG is licensed and

commercially available. SYN023 was tolerated acceptably in the initial human study thus enrollment of this study may be parallel between the different study groups. Vaccination will occur within 75 minutes after Study Drug administration. RVi, RVa, SYN023 and RIG will be administered by intramuscular injection. Generally antibodies should be administered on the right side of the body and vaccinations on the left side of the body to avoid administration in the same site.

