#### 3.6.3.1 Pre-Study Study Drug and Post-Study Drug Administration Clinical Monitoring of Subjects

Hypersensitivity reactions are a potential adverse effect of all medicinal products administered in this protocol including monoclonal antibodies. Allergic reactions to vaccination are possible, therefore, appropriate drugs and medical equipment to treat acute anaphylactic reactions must be immediately available and a medically qualified study team member trained to recognize and treat anaphylaxis must be present in the clinic during the entire vaccination procedure and post-vaccination monitoring period. Appropriate drugs include intravenous fluids, epinephrine, antihistamines, corticosteroids, inhaled oxygen and drugs required for the treatment of cardiac arrest such as antiarrhythmics and pressors. Appropriate equipment includes devices for blood pressure monitoring, oximetry, maintenance of airway and intratracheal intubation and, removal of secretions and cardiac defibrillation.

Grade  $\geq 3$  hypersensitivity reactions are Immediately Reportable Events.

Subjects will have vital signs and oximetry taken prior to Study Drug administration. Before after and between each medicinal product administration vital signs and oximetry will be monitored every 30 minutes At every clinical contact the subject will be asked how they are feeling and if they have noticed any new adverse symptoms or manifestations.

Subjects will remain in the clinic under close observation for at least 240 minutes after receiving rabies vaccination that is administered after Study Drug. Vital signs and oximetry will be repeated every 30 minutes during the 240 minute monitoring period before subjects leave the clinic.

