### **7.6.2 Clinical Laboratory and Vital Sign Parameters**

For each clinical laboratory parameter and vital sign parameter prespecified in the protocol, summary statistics for continuous parameters will be presented by treatment regimen for all pre- and post-Study Drug assessments and for change from pre-Study Drug to post-Study Drug assessments.

Statistical methods: Analysis of Safety

Safety analyses will be performed using the Safety Population, as defined in Section 7.1. Count and percent summaries will be presented by treatment group for all subjects.

Descriptive statistics (number of subjects, mean, standard deviation, percent coefficient of variation, median, minimum, and maximum) will be used to summarize all safety and laboratory data.

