**Baseline Visit (Study Day 0)**

- Verify eligibility by review of inclusion/exclusion criteria
- Conduct focused physical examination including weight
- Insure that results of Serum  $\beta$ HCG are negative
- Record vital signs and oximetry
- Record interval history
- Record concurrent medications
- Collect urine sample for urinalysis
- Insure that blood samples collected for:
  - Serum chemistry: total bilirubin, BUN, CPK, troponin, creatinine, ALT, AST, alkaline phosphatase, sodium, potassium, chloride, bicarbonate calcium

- 
- Hematology: CBC including differential and platelets
  - Clotting studies: PTT and prothrombin INR
  - Anti-SYN023 antibodies
  - SYN023 antibody levels
  - Rabies Virus Inhibitory Serum Activity
  - Administer Study Drug (RIG or SYN023) on Right side of body
  - Within approximately 75 minutes administer RVa or RVi on Left side of body
  - Distribute diary and thermometer and instruct subject in their use
  - Assess patient for AEs and SAEs
  - Perform vital signs & oximetry every 30 minutes during the 240 minutes of observation prior to discharge

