9.2.2 Unsolicited Adverse Events

Unsolicited AEs are any unsolicited unfavorable or unintended sign, symptom, disease, syndrome, abnormal laboratory finding, or concurrent illness that emerges or worsens after receipt of study vaccine relative to the subject's pre-treatment baseline, whether or not it is considered to be related to the medicinal product. The unsolicited AE reporting period begins with the day of vaccination (Day 0) through Day 42 inclusively. Additionally, any solicited AE (local or systemic) that persist beyond Day 28 will be recorded as an unsolicited AE.

Summary of descriptive statistics for unsolicited AEs (incidence of subjects with percentages and incidence of unsolicited AEs) will be presented by treatment and overall, SOC, PT, by investigator-assessed relationship (Not Related, Unlikely Related, Possible, Probable, and Definite) and severity (Mild, Moderate, and Severe). For incidence of subject calculations, each subject may only contribute once to each of the incidence rates, for an unsolicited AE following a given treatment, regardless of the number of occurrences; the highest severity or highest relationship will be presented, as appropriate.

In each table, SOC will be presented in descending order of overall incidence rate in terms of frequency of subjects and then in frequency of events (alphabetical order will be used in case of equal rates). For each SOC, PT will be presented the same way.

All unsolicited AEs will be listed.

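### Read literally, SAP 9.4 allows a vital-sign reading taken after SYN023 or RIG to serve as baseline, contrary to protocol 7.6.2

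*SAP*

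**What the plan says.** **SAP.** Section 9.4 sets the reference point for change in vital signs: "Baseline will be defined as the last results (scheduled or unscheduled) obtained prior to the first study vaccine administration". Sections 9.3 (laboratory) and 9.5 (ECG) use the same sentence. Section 3.3 uses the word vaccine for Imovax and RabAvert, each given five times from Day 0.

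**Protocol, order of products.** Section 3.5 treats SYN023 and RIG as the study drugs, separate from the two vaccines, and states: "Vaccination will occur within 75 minutes after Study Drug administration". Appendix A has the same order for Day 0: Study Drug, then "Within approximately 75 minutes administer RVa or RVi on Left side of body".

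**Protocol, vital signs.** Section 3.6.3.1 requires a pre-drug reading ("Subjects will have vital signs and oximetry taken prior to Study Drug administration") and continues: "Before after and between each medicinal product administration vital signs and oximetry will be monitored every 30 minutes".

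**Protocol, analysis.** Section 7.6.2 asks for summary statistics at each assessment and "for change from pre-Study Drug to post-Study Drug assessments".

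**The concern.** The SAP ties baseline to the vaccine, while the protocol ties it to Study Drug. On Day 0 these are different moments, and the protocol calls for vital signs between them. A programmer who follows the SAP as written would take the latest reading before the vaccine, even if SYN023 or RIG had already been injected.

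The period between the two injections is the first in which an acute reaction to the antibody could show in blood pressure, pulse or temperature, and protocol 3.6.3.1 names hypersensitivity as a possible effect of every product given. Comparing safety is a secondary objective, and SAP section 9 plans no inferential safety analysis, so the descriptive tables carry that comparison. A baseline that already contains the early response to the antibody would distort the change-from-baseline tables among them.

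**Working it through.** The plan states no figure to reproduce. The check is a timeline count, followed by simple algebra.

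**1. Which readings can fall between Study Drug and vaccine?** The inputs are a maximum gap of 75 minutes (protocol 3.5) and a reading every 30 minutes (protocol 3.6.3.1). I assume the 30-minute clock starts at Study Drug. The number of interval readings after Study Drug and up to the vaccine is the whole-number part of gap/30. At the maximum, 75/30 = 2.5, which gives 2.

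| Gap (min) | Readings in the gap | Reading the SAP rule would select |
|---|---|---|
| 15 | 0 | pre-drug |
| 30 | 1 | 30 min post-drug |
| 45 | 1 | 30 min post-drug |
| 60 | 2 | 60 min post-drug |
| 75 | 2 | 60 min post-drug |

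With baseline set before Study Drug, the number of eligible post-drug readings is 0 in every row.

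**2. What does this do to change from baseline?** Let d be an acute shift after Study Drug that is present at the selected reading. The SAP baseline is then the pre-drug value plus d, so

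SAP change = (change from pre-drug) − d.

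The values of d below are illustrative and are not in the documents (mmHg).

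| d | Course of the shift | Change from pre-drug | SAP change |
|---|---|---|---|
| −5 | persists after vaccine | −5 | 0 |
| −5 | resolved by Day 1 | 0 | +5 |
| −10 | persists after vaccine | −10 | 0 |
| −10 | resolved by Day 1 | 0 | +10 |
| −20 | persists after vaccine | −20 | 0 |
| −20 | resolved by Day 1 | 0 | +20 |

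The error therefore runs in two ways. A persisting shift disappears, and a resolved one reappears with the opposite sign.

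**3. How much of a group mean is affected?** If a proportion p of a group has a post-drug reading as baseline, and d is the same in all of them, the group mean change is off by −p × d. The documents do not give p, so its range is 0 to 1. For d = −10 the error in the mean lies between 0 and +10 mmHg. Where p is the same in the SYN023 and RIG groups, the error in their difference is −p × (d for SYN023 − d for RIG). What is lost is a difference in acute effect between the two products.

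**4. Do laboratory tests and ECG share the problem?** The baseline sentence is the same but the timing is not. Protocol 3.1 and 3.2.5 place scheduled Day 0 blood sampling ahead of Study Drug and vaccine. A footnote to Table 3.1-1 does the same for ECG and urinalysis, but the vital-signs row does not carry it. For laboratory tests and ECG, only an unscheduled result in the gap could replace the pre-drug value.

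**5. Is the departure declared?** SAP section 4 lists only changes to the pharmacodynamic parameters. It says nothing about baseline.

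**The case against.** The strongest reply is that this is a slip in terminology. The SAP uses study vaccine loosely elsewhere: section 8.6, under a heading about Study Drug, lists vaccine administration details. Section 9.2 defines an adverse event from receipt of study drug, whereas 9.2.2 repeats the definition as "emerges or worsens after receipt of study vaccine relative to the subject's pre-treatment baseline". That explanation is plausible, and it counts against reading the rule as a deliberate choice. It does not remove the ambiguity. SAP 3.3 reserves vaccine for the five-dose products, so the natural literal meaning is the first Imovax or RabAvert dose, and the SAP offers no other definition.

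Three stronger readings are tempting, and the documents do not support them.

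- *Every subject's baseline is affected.* The 75 minutes is a maximum, and no distribution of gaps is given. Nor do the documents say whether the 30-minute monitoring readings enter the analysis dataset. SAP 9.4 lists vital signs by study day, and Table 3.1-1 has a single Day 0 entry. Appendix A mentions 30-minute readings only for the 240-minute observation period, which section 3.6.3.1 counts from vaccination. However, the SAP's inclusion of unscheduled results does not exclude readings in the gap.
- *Acute reactions would be hidden.* Adverse events are judged against the pre-treatment state (protocol 5.3, SAP 9.2). Toxicity grades for vital signs use fixed limits (protocol Appendix E). SAP 9.4 also summarises absolute values and lists every result. The pausing and stopping rules in protocol section 6 do not use change from the SAP baseline.
- *All safety baselines are compromised.* Step 4 of the working shows that scheduled laboratory tests and ECGs precede the injections.

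**Conclusion.** The point holds for vital signs. As worded, SAP 9.4 permits a post-drug baseline, which conflicts with protocol 7.6.2 and is not declared as a change. Up to two readings are candidates when the gap is 60 to 75 minutes, and none when it is under 30 minutes.

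The consequence is limited to descriptive change-from-baseline summaries of vital signs. It would be wrong to describe the bias simply as towards no effect, because a shift that has resolved produces a false change in the other direction.

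The conclusion rests on a literal reading of vaccine, on the 30-minute clock starting at Study Drug, and on readings in the gap reaching the analysis dataset. The documents leave the last of these open. Sample size, power and alpha are not involved.

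**What to change.** In SAP 9.4, define baseline as the last result, scheduled or unscheduled, before administration of Study Drug (SYN023 or RIG). State that readings between Study Drug and the first vaccine dose are post-dose.

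Use the same definition in 9.3 and 9.5 for consistency; there it matters only for an unscheduled result in the gap. In 9.2.2, replacing the reference to vaccine with Study Drug is harmonisation with 9.2 and changes nothing of substance.

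The cost is a few words in the SAP, best made before the tables are programmed. No procedure changes, because the pre-drug reading is already required by protocol 3.6.3.1.

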9.5 Electrocardiogram

ECGs measurements will be performed at the time of screening, on Day 0, Day 1, Day 3, Day 7, Day 14, Day 28, and 112. The quantitative ECG measurements are heart rate (HR) or ventricular rate (VR), PR interval, QRS interval, QT interval, QTcB interval (Bazett formula correction), and QTcF interval (Fridericia's formula correction).

Descriptive statistics (mean, median, SD, Min, Max, and sample size) will be presented overall for screening and by the associated current treatment for on-study measurements and each ECG measurement. Descriptive statistics for change from baseline for on-study measurements will also be presented. Baseline will be defined as the last results (scheduled or unscheduled) obtained prior to the first study vaccine administration. Results from on-study repeat tests will not be included in the summary statistics unless the repeat was required (and documented as such) due to technical reasons or an invalid initial result.

A listing of all ECG results will be presented.

10. Efficacy/Pharmacodynamic (Serum Rabies Virus Neutralizing Activity) Analyses

Shells for all summary descriptive statistic tables and listings referred to in this section are displayed in a separate document; the shells may be revised as they are presented to illustrate the general layout of data to be included in the final report.

Efficacy/PD analyses will be performed on PP population.

10.1 Handling of the BLQ and the No Reportable Concentration Values

All concentration values below the lower limit of quantification (BLQ) will be set to zero. Samples with no reportable value occurring prior to the first dosing will be replaced by “0.00” otherwise they will be set to missing for tabulation, graphical representation and calculation purposes.

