**Table 1.5-1 Mean RVNA activity in IU by dose level in Phase I study of SYN023. Five subjects in each group.**

Dose Level mg/kg	Study Day							
	0	1	3	7	14	28	35	84
0.3	0.00 ± 0.00	2.70 ± 0.43	3.68 ± 0.56	4.44 ± 1.09	3.78 ± 0.41	2.82 ± 0.61	1.82 ± 0.93	0.22 ± 0.25
1.0	0.00 ± 0.00	8.88 ± 3.13	10.02 ± 2.07	17.00 ± 8.81	11.2 ± 3.24	10.3 ± 3.37	11.64 ± 3.86	2.22 ± 1.06
2.0	0.02 ± 0.00	13.40 ± 8.19	27.60 ± 3.31	35.00 ± 2.40	35.6 ± 3.85	13.80 ± 7.61	10.14 ± 2.12	3.76 ± 1.07

These results are graphically presented for the lowest dose group as means ± 95% confidence interval (Figure 1.5-1). Rabies neutralizing activity from IM injection Study Day 0 was measurable and several-fold above the minimum inhibitory level of 0.5 IU/mL on Study Days 1, 3, 7, 14 and 28.

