### **7.7 Sample Size Considerations**

The sample size for this Phase 2 study was selected based on requirement to consider noninferiority of the efficacy parameter, RVNA. The power analysis was performed in SAS 9.2 using the power procedure for noninferiority testing under the assumption of the sample size of 40 per group and likely margin corresponding to SYN023 being no less than 10% lower than RIG. Based on earlier studies, the mean RVNA for 0.3 mg/kg SYN023 of 20 with CV of 15-25% are reasonable. For assumed underlying differences of 0 to 1 IU/mL, there is over 80% to conclude non-inferiority of RVNA level at a specified time point. The sample size of 40 per treatment group should be sufficient to address the efficacy objectives of the study.

The assumptions that a difference of 2 or less is considered unimportant (the approximate mean value for 0.3mg/kg SYN023 of 20 was used), with the range in mean difference from -1 to 1, standard deviation of 3 and power of 0.8, the required sample size of 29 is needed to declare that the new treatment (SYN023) is not more tolerably inferior to the previous treatment (RIG). Also, the power analysis was performed for the sample size of 40, standard deviation 3 and the mean difference of 2. This resulted in the power of 0.838. The above results from the sample size and power analysis showed that the sample size of 40 should be sufficiently powered for this study.

Also, a power analysis for non-inferiority of the AUCs was performed using “PowerTOST”, an R CRAN package run under Rstudio version 0.99.491. Under the assumption of a lower non-inferiority bound of 0.9 (corresponding to SYN023 being no less than 10% lower than RIG), the selected sample size of 40 per group would provide over 80% power assuming a CV of 10-20%.

If no SAEs are observed among subjects in each dose group and the 40 subjects in the 3 dose groups combined, the one-sided exact upper 95% confidence bounds on the rate of SAE occurrence will be 45% and 18%, respectively.

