10.3 Efficacy/Pharmacodynamic Parameters

A total of 10 blood samples will be drawn from each subject for efficacy/PD analyses. Blood samples will be collected on Day 0, Day 1, Day 3, Day 7, Day 14, Day 28, Day 35, Day 42, Day 84, and Day 112.

RVNA will be used to calculate the following parameters by standard non-compartmental methods:

AUEC_{0-t}: area under the effect-time curve above the minimum rabies virus neutralizing activity threshold (0.5 IU/mL) from time 0 to the last measurable concentration, calculated using the linear trapezoidal method. Unit will be Day*IU/mL.

AUEC₀₋₇: area under the effect-time curve above the minimum rabies virus neutralizing activity threshold (0.5 IU/mL) from time 0 to 7 days, calculated using the linear trapezoidal method. In case where the 7 days RVNA value is missing, AUEC₀₋₇ will be interpolated at the discretion of the pharmacokineticist. Unit will be Day*IU/mL.

- AUEC₀₋₁₄: area under the effect-time curve above the minimum rabies virus neutralizing activity threshold (0.5 IU/mL) from time 0 to 14 days, calculated using the linear trapezoidal method. In case where the 14 days RVNA value is missing, AUEC₀₋₁₄ will be interpolated at the discretion of the pharmacokineticist. Unit will be Day*IU/mL.
- AUEC_{14-t}: area under the effect-time curve above the minimum rabies virus neutralizing activity threshold (0.5 IU/mL) from time 14 days to the last measurable concentration, calculated using the linear trapezoidal method. In case where the 14 days RVNA value is missing, AUEC_{14-t} will be interpolated at the discretion of the pharmacokineticist. Unit will be Day*IU/mL.
- AUEC₁₄₋₃₅: area under the effect-time curve above the minimum rabies virus neutralizing activity threshold (0.5 IU/mL) from time 14 days to 35 days, calculated using the linear trapezoidal method. In case where the 14 days or 35 days RVNA value is missing, AUEC₁₄₋₃₅ will be interpolated at the discretion of the pharmacokineticist. Unit will be Day*IU/mL.
- E_{max}: maximum observed effect. Unit will be IU/mL.
- T_{max,E}: time of observed E_{max}. Unit will be Day.

Some efficacy/PD parameters may not be calculated for all or some subjects, at the discretion of the inVentiv pharmacokineticist, if the concentration data is not deemed to be amenable to evaluation. Explanations for efficacy/PD parameters that could not be estimated will be provided in the CSR.

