10.4 Statistical Analyses

Individual and mean RVNA versus time curves will be presented using linear and semi-log scales for RVNA. Listings and descriptive statistics (number of observations, arithmetic mean, SD, coefficient of variation [CV%], median, Min, Max, geometric mean, and the percentage of subjects with RVNA values above 0.5 IU/mL [% > 0.5 IU/mL]) of the RVNA versus time as well as all PD parameters will be provided for each treatment.

For inferential analyses, data will be analysed as a two-factor factorial design. The two factors will be Vaccine including 2 levels (RVi and RVa) and Conmed including 2 levels (RIG and SYN023) as described in Table 10-1.

Table10-1: Two-factor factorial design with Vaccine and Immune Globulin (IG) as factors

		IG	
		RIG	SYN023
Vaccine	RVi	N _A =40	N _C =40
	RVa	N _B =40	N _D =40

Where N_X is the number of subjects planned to be dosed for Treatment X (X=A, B, C, D).

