10.4.1 Similarity Acceptance

Using GLM procedures in SAS[®], ANOVA will be performed on untransformed $T_{\max,E}$ and ln-transformed $AUEC_{0-t}$, $AUEC_{0-7}$, $AUEC_{0-14}$, $AUEC_{14-t}$, $AUEC_{14-35}$, and E_{\max} at the alpha level of 0.05. Factors incorporated in the model will include: Vaccine, IG, and Vaccine*IG. Vaccine, IG, and Vaccine*IG will be tested against the residual mean square error. In the case of a non-statistically significant Vaccine*IG interaction term, the analysis will be rerun excluding this term from the ANOVA model in order to obtain ratios and confidence intervals where appropriate. In the case of statistically significant Vaccine*IG interaction term, the analysis will be rerun for each vaccine separately. All sums of squares (Types I, II, III and IV) will be reported. Probability (p) values will be derived from Type III sums of squares. Coefficients of variation (CV%) will be estimated.

Based on pairwise comparisons of the ln-transformed $AUEC_{0-t}$, $AUEC_{14-t}$, and E_{\max} data, the ratio (RIG/SYN023) of the geometric least-squares means, calculated according to the formula “ $e^{(X-Y)} * 100$ ”, as well as the corresponding 90% geometric confidence intervals will be determined.

For $AUEC_{14-t}$, a statistically significant Vaccine*Conmed interaction term will be interpreted as a possible interference of RIG or SYN023 on the vaccines. In this case, each vaccine will be investigated separately.

Additional analyses may be performed.

Criteria for Similarity

Considering PP population, the 90% geometric confidence intervals of the ratio (RIG/SYN023) of least-squares means from the ANOVA of the ln-transformed $AUEC_{0-t}$ must be within 80.00% to 125.00%.

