10.4.2 RIG vs. SYN023 Comparison by Timepoint

Using GLM procedures in SAS[®], ANOVA will be performed separately on ln-transformed RVNA at Day 1, Day 3, Day 7, Day 14, Day 28, Day 35, Day 42, Day 84, and Day 112 at the alpha level of 0.05. Factors incorporated in the model will include: Vaccine, Conmed, and Vaccine*Conmed. Vaccine, Conmed, and Vaccine*Conmed will be tested against the residual mean square error. In the case of a non-statistically significant Vaccine*Conmed interaction term, the analysis will be rerun excluding this term from the ANOVA model in order to obtain ratios and confidence intervals where appropriate. In the case of statistically significant Vaccine*Conmed interaction term, the analysis will be rerun for each vaccine separately. All sums of squares (Types I, II, III and IV) will be reported. Probability (p) values will be derived from Type III sums of squares. Coefficients of variation (CV%) will be estimated.

Based on pairwise comparisons of the ln-transformed Day 1, Day 3, Day 7, Day 14, Day 28, Day 35, Day 42, Day 84, and Day 112 data, the ratio (RIG/SYN023) of the geometric least-squares means, calculated according to the formula “ $e^{(X-Y)} * 100$ ”, as well as the corresponding 90% and 95% geometric confidence intervals will be determined.

Additional analyses may be performed.

11. Immunogenicity: Anti-SYN023 Antibodies Analyses

Shells for all summary descriptive statistic tables and listings referred to in this section are displayed in a separate document; the shells may be revised as they are presented to illustrate the general layout of data to be included in the final report.

Immunogenicity analyses will be performed on PP population. No inferential analysis will be done.

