12.4 Statistical Analyses

No statistical analysis is planned on samples obtained from subjects who received Treatment A (RVi + RIG) and Treatment B (RVa + RIG), but any cases of detectable and quantifiable levels observed in these subjects (for those who were analyzed) will be addressed descriptively in the PK report.

For Treatment C (RVi + SYN023) and Treatment D (RVa + SYN023), individual and mean serum concentration versus time curves will be presented using linear and semi-log scales for SYN023. Listings and descriptive statistics (number of observations, arithmetic mean, SD, coefficient of variation [CV%], median, Min, Max, and geometric mean) of the concentrations versus time as well as all PK parameters will be provided for each treatment.

Only descriptive statistics will be used to compare Treatment C and Treatment D.

A table and figures (individual and mean versus time curves) presenting RVNA on SYN023 concentrations ratios over time will be provided. For a given scheduled timepoint, the ratio will be defined as

$$\text{Ratio} = \frac{\text{RVNA}}{\text{CTB011 concentration} + \text{CTB012 concentration}}$$

No attempt will be made to extrapolate or interpolate to correct any concentrations in case of time deviations for ratios calculation. Results will be presented using scheduled times.

Additional analyses may be performed.

13. Data Handling

Safety, tolerability, immunogenicity, efficacy/PD and PK data will be received as SAS[®] datasets from the data management facility

14. Handling of Missing Data

Only observed data will be used in the data analysis except for concentration values BLQ and samples with no reportable value occurring prior to dosing as described in Section 10, 11, and 12. No attempt will be made to extrapolate or interpolate estimates for missing data.

15. Software to be Used

Efficacy/PD and PK analysis will be performed using Phoenix WinNonlin[®] version 6.4, which are validated for bioequivalence/bioavailability studies by inVentiv. The inferential statistical analyses, the safety data tables and listings, the efficacy/PD data tables and listings, the immunogenicity data tables and listings as well as PK tables and listings will be created using SAS[®], release 9.2 or a higher version. PK figures will be created using R version 3.2.2 (or

higher). The PK report text will be created using Microsoft® Office Word 2010, or a higher version.

16. Reference List

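### Below-LLOQ RVNA is set to zero and then log-transformed with no rule for zeros, so low-outcome subjects drop out of secondary early RIG/SYN023 comparisons (minor)

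*SAP*

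**What the plan says.** **By-day RVNA.** SAP 10.1, which governs the RVNA data, states: "All concentration values below the lower limit of quantification (BLQ) will be set to zero". Post-dose samples with no reportable value are a separate category and become missing. SAP Section 14 keeps the two apart: "Only observed data will be used in the data analysis except for concentration values BLQ". A BLQ result therefore enters the analysis as a numeric zero. SAP 10.4.2 then specifies: "ANOVA will be performed separately on ln-transformed RVNA at Day 1, Day 3, Day 7, Day 14", and likewise for the later days to Day 112, with RIG/SYN023 geometric mean ratios and 90% and 95% CIs.

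**AUEC0-7.** SAP 10.3 defines it as the area above the "threshold (0.5 IU/mL) from time 0 to 7 days, calculated using the linear trapezoidal method". SAP 10.4.1 includes it among the ln-transformed parameters to be tested by ANOVA. That section plans ratios and 90% CIs only for AUEC0-t, AUEC14-t and Emax.

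**Status.** SAP Section 5 makes AUEC0-t primary and all other PD parameters secondary. The only acceptance criterion, in SAP 10.4.1, is on AUEC0-t.

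**What stays visible.** SAP 10.4 plans listings, number of observations, minimum and "the percentage of subjects with RVNA values above 0.5 IU/mL" by treatment and time.

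No offset, substitution or censoring rule for zeros before the log appears in SAP 10.1, 10.3, 10.4 or 14.

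**The concern.** The plan creates zeros and then applies a transformation that is undefined at zero. In SAS the log becomes missing and GLM drops the record. The exclusion depends on the outcome, so the subjects left in that model are no longer the randomised comparison.

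The exclusion is unlikely to be balanced. Protocol 1.5 says vaccine-induced RVNA is unlikely from Day 0 to Day 7, so early values mainly reflect the passive antibody. SYN023 0.3 mg/kg averaged 2.70 IU/mL on Day 1 in Phase 1. Any early zeros would probably be in the RIG arms. Dropping them raises the RIG geometric mean and the RIG/SYN023 ratio, which works against SYN023.

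At stake are the early by-day ratios, which are the SAP's only RIG/SYN023 ratios by time point, and the AUEC0-7 ANOVA tests, including Vaccine*IG. Protocol 2.2 and 7.3 define pharmacodynamic efficacy at any time point through Day 35, so the early days are of interest. Protocol 3.4 says the statistician is unblinded, so a rule for zeros chosen later could be chosen with treatment known.

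**Working it through.** **Plan figure on variability.** Protocol 7.7 says "the mean RVNA for 0.3 mg/kg SYN023 of 20 with CV of 15-25% are reasonable". The table headed "Mean RVNA activity in IU by dose level in Phase I study of SYN023" gives, at 0.3 mg/kg, 2.70 ± 0.43, 3.68 ± 0.56 and 4.44 ± 1.09 on Days 1, 3 and 7. If ± is an SD, the CVs are 0.43/2.70 = 16%, 0.56/3.68 = 15% and 1.09/4.44 = 25%, which reproduces the planning range. CVs of 50% and 80% below are stress cases.

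**Inputs not in the documents.** The LLOQ and all RIG RVNA levels. Both are assumed and varied.

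**Cap on the LLOQ, if the same assay is used.** The 0.3 mg/kg Day 84 cell is 0.22 ± 0.25 with n = 5. Under the SD reading the sum is 1.10 and the sum of squares is 4(0.25²) + 5(0.22²) = 0.492. Two non-zero values are impossible, since they need at least 1.10²/2 = 0.605. With three, the smallest is largest when two equal x: 2x² + (1.10 − 2x)² = 0.492, so x = 0.245. Carrying the rounding of both figures gives 0.266, say 0.27. If ± is a 95% CI half-width, the cap is 0.374, reached only with three nearly equal values. The 2.0 mg/kg Day 0 cell (0.02 ± 0.00) would imply at most 0.025, although Protocol 1.5 says all subjects lacked RVNA before dosing.

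**By-day bias.** Assume log-normal RVNA with geometric mean G and s = √ln(1 + CV²), and zeros only in the RIG arms. With z = ln(LLOQ/G)/s, the BLQ share is p = Φ(z). Dropping those subjects inflates the ratio by exp(s·φ(z)/(1 − p)) − 1. Entering LLOQ/2 instead changes it by exp(s·φ(z) + p·ln(LLOQ/(2G))) − 1.

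For G = 0.5 and LLOQ = 0.27:

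| CV | s | z | BLQ share | zeros dropped | LLOQ/2 |
|---|---|---|---|---|---|
| 15% | 0.149 | −4.13 | 0% | 0% | 0% |
| 25% | 0.246 | −2.50 | 0.6% | +0.4% | −0.4% |
| 50% | 0.472 | −1.30 | 9.6% | +9% | −4% |
| 80% | 0.703 | −0.88 | 19.0% | +27% | −6% |

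Other settings, zeros dropped, CV 15/25/50/80%:
- G 0.5, LLOQ 0.2: 0/0/3/14%.
- G 0.5, LLOQ 0.1: 0/0/0.1/2%.
- G 0.5, LLOQ 0.025: nil.
- G 0.8, LLOQ 0.27: 0/0/1/9%.

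At the extreme cap of 0.374 with G 0.5, z is −1.95 and −1.18 at CV 15% and 25%, and the inflation is about 1% and 6%.

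**Against the 10% rule.** SYN023 no more than 10% lower means RIG/SYN023 up to 1/0.9 = 1.11. Take RIG at 0.5 and SYN023 at mean 2.70 with CV 16%, so its geometric mean is 2.70/√(1 + 0.16²) = 2.67. The true ratio is 0.5/2.67 = 0.19. The worst inflation in the table, 27%, takes it to 0.24, far below 1.11.

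**Zero AUEC0-7.** A profile of 0, 0.20, 0.30, 0.45 on Days 0, 1, 3, 7 never exceeds 0.5 and scores exactly zero. The share of such RIG subjects is the trivariate normal probability that Days 1, 3 and 7 are all at or below 0.5, with constant G and within-subject correlation 0.5 to 0.9. No LLOQ is needed.

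| Assumed RIG geometric mean | CV 15-25% | CV 50-80% |
|---|---|---|
| 0.5 | 25-39% | 25-39% |
| 0.6 | 2-15% | 13-30% |
| 0.8 | 0-1.3% | 3-17% |
| 1.0 | 0-0.1% | 1-10% |

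At 0.5 this is 20 to 31 of the 80 RIG subjects.

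**SYN023 for comparison.** The Phase 1 means (0, 2.70, 3.68, 4.44) give 0.90 + 5.38 + 14.24 = 20.5 Day*IU/mL above 0.5, so zeros are not expected there.

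**The case against.** **The material figures rest on assumption.** At the documents' CV, the by-day bias at LLOQ 0.27 is 0-0.4%; 9% to 27% needs a stress-case CV. No passage supports a RIG geometric mean of 0.5 or 0.6. Protocol 7.7 works with a difference of 0 to 1 IU/mL. Carried to Day 1, RIG would be 2.70 − 1 = 1.7, and the chance of a value at or below 0.5 at CV 25% would be Φ(ln(0.5/1.7)/0.246), about 3 in 10 million. This stands as a reason the effect may be nil. It does not settle the matter, because that difference was set around a mean of 20, not an early value.

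**Low values are not hidden.** This stands. With the listings, number of observations and percentage above 0.5 IU/mL, a reader can count the zeros. The plan lacks only a stated rule and a direct count of subjects leaving each ln model.

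**The protocol has a rank test that tolerates zeros.** Protocol 7.3 pairs the 10% margin with a Wilcoxon test, and SAP Section 4 does not list its removal. But the test is optional, its example days are 14 and 28, and SAP Section 10 does not carry it forward. It does not cover Days 1 to 7.

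**The discretion clause in SAP 10.3 covers it.** It does not. That clause is for data not suited to evaluation, and a zero area is a properly computed value.

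**Stronger readings.** A reader might infer that the similarity conclusion is at risk. The documents do not support this: AUEC0-t is zero only if RVNA never exceeds 0.5 through Day 112, and Protocol 1.1 expects adequate activity in virtually all vaccinees by Day 14. A reader might also infer a wrong AUEC0-7 ratio, but none is planned.

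**Conclusion.** The gap is real and minor. The SAP's rules, as written, remove subjects for a low outcome from the by-day ln RVNA ratios and from the ln AUEC0-7 ANOVA. The likely direction is against SYN023, provided zeros fall mainly in the RIG arms.

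The size is conditional and may be nil. For the by-day ratios it is at most about 0.4% at CV 15-25%, given an assumed RIG geometric mean of 0.5 and LLOQ of 0.27. It is larger only with a higher LLOQ or a CV well above the protocol's. AUEC0-7 is more exposed: many RIG subjects could score zero at a geometric mean near 0.5, but almost none at 0.8 or more at the protocol's CV. For AUEC0-7 only the ANOVA tests are affected. Neither the AUEC0-t criterion nor the trial's conclusion is expected to change. Confidence is medium, because the LLOQ and the RIG levels are unknown.

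**What to change.** - **SAP 10.1:** state the LLOQ, and limit the zero rule to listings, arithmetic summaries and AUEC calculation.
- **SAP 10.4.2:** keep the planned ANOVA with BLQ values entered as LLOQ/2. On any day with BLQ values, add a left-censored log-normal model as a sensitivity analysis, with variance allowed to differ by IG arm.
- **SAP 10.4.1:** add a rank test of AUEC0-7, stratified by vaccine, that keeps zeros. Place it next to the planned ANOVA so that the Vaccine*IG test is retained.
- **Tables:** report BLQ counts by arm and day, and zero-AUEC0-7 counts by arm.

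**Cost.** A few SAP sentences, one count table and minor programming before database lock; no new data. LLOQ/2 is itself biased: it puts the ratio about 4-6% too low at 10-19% BLQ, against about 9-27% too high when zeros are dropped. The censored model assumes log-normality below the LLOQ. It needs arm-specific variance because, in simulation with RIG CV 80% and SYN023 CV 16%, a common variance left a bias of roughly 2.5-3.5%. The rank test gives no interaction test, so it supplements the ANOVA and does not replace it.
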